 - Inability to re-treat patient within 2 wks of scheduled treatment due to treatment-related adverse event
 - Inability to deliver all doses of Lenalidomide and or Everolimus during the first cycle due to an unexpected drug-related toxicity (if toxicity is an

expected toxicity as per current package insert, then it will not be considered a DLT). These subjects should be discontinued from the study

In the event of study discontinuation prior to completing the entire first treatment cycle for reasons other than DLT, the affected subject will be considered inevaluable for toxicity and will be replaced by another subject to be treated at the same dose-level.

Secondary:

- Significant drug-drug interaction will be determined through pharmacokinetic analysis for parent drug and metabolites (the following PK parameters will be estimated and reported for each agent according to dose level – (AUC_{0→t}) Area under the concentration-time curve from the time of dosing to the time of the last observation; (AUC_{0→∞}) Area under the concentration-time curve from the time of dosing extrapolated to infinity; (C_{max}) Maximum serum concentration observed postdose; (T_{max}) Time point at which the C_{max} occurs; (t_{1/2}) Elimination half-life, determined as 0.693/λ_z)
- The frequency of achieving a complete plus partial response to the 2 drug combination by dose cohort. Response will be assessed by cross sectional imaging after every 2 cycles and will be categorized according to RECIST 1.1 criteria.

Correlative:

- Mean change in immunological biomarkers at baseline, after 1 cycle of protocol directed therapy and at disease progression by dose cohort
- Mean change in plasma levels of inflammatory markers at baseline, after 1 completed cycle of therapy and at disease progression
- Plasma level of cathepsin G at baseline, after 1 cycle of therapy and following the first diagnosis of venous thromboembolic disease

STUDY DURATION: 18-24 months	TOTAL SAMPLE SIZE: 45

DOSING REGIMEN(S):
 
According to dose cohort:
 
Lenalidomide once daily days 1-28 of a 28 day cycle
 
Everolimus once daily continuously (day 1-28)
	
DRUG SUPPLIES:
 
For study participants, Celgene Corporation will provide lenalidomide at no charge through the RevAssist® program.
 
Everolimus will be supplied by Novartis Pharmaceuticals Corporation and dispensed through the Investigational Drug Pharmacy

2 Schedule of Study Assessments *

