5.3.5 Non Clinical Toxicology

Carcinogenesis, Mutagenesis, Impairment of Fertility

Administration of everolimus for up to 2 years did not indicate oncogenic potential in mice and rats up to the highest doses tested (0.9 mg/kg) corresponding respectively to 4.3 and 0.2 times the estimated clinical exposure (AUC_{0-24h}) at the recommended human dose of 10 mg daily. Everolimus was not genotoxic in a battery of in vitro assays (Ames mutation test in Salmonella, mutation test in L5178Y mouse lymphoma cells, and chromosome aberration assay in V79 Chinese hamster cells). Everolimus was not genotoxic in an in vivo mouse bone marrow micronucleus test at doses up to 500 mg/kg/day (1500 mg/m²/day, approximately 255-fold the recommended human dose, based on the body surface area), administered as two doses, 24 hours apart. Based on non-clinical findings, male fertility may be compromised by treatment with AFINITOR. In a 13-week male fertility study in rats, testicular morphology was affected at 0.5 mg/kg and above, and sperm motility, sperm count, and plasma testosterone levels were diminished at 5 mg/kg, which resulted in infertility at 5 mg/kg. Effects on male fertility occurred at the AUC_{0-24h} values below that of therapeutic exposure (approximately 10%-81% of the AUC_{0-24h} in patients receiving the recommended dose of 10 mg daily). After a 10-13 week non-treatment period, the fertility index increased from zero (infertility) to 60% (12/20 mated

females were pregnant). Oral doses of everolimus in female rats at ≥ 0.1 mg/kg (approximately 4% the AUC_{0-24h} in patients receiving the recommended dose of 10 mg daily) resulted in increases in pre-implantation loss, suggesting that the drug may reduce female fertility. Everolimus crossed the placenta and was toxic to the conceptus.

In safety pharmacology studies, everolimus was devoid of relevant effects on vital functions including the cardiovascular, respiratory and nervous systems. Everolimus had no influence on QT interval prolongation. Furthermore, everolimus showed no antigenic potential. Although everolimus passes the blood-brain barrier, there was no indication of relevant changes in the behavior of rodents, even after single oral doses up to 2000 mg/kg or after repeated administration at up to 40 mg/kg/day. Based on these findings, the potential of everolimus to affect vital functions in patients is low.

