5.7.3 Instructions for dose modifications or interruption during a cycle

This information is meant to assist in dose modification for individual study participant who experienced a treatment-related toxicity. The dose escalation schema for the study cohort will proceed as described under the escalation schema (refer Table 1, Section 5.1).

In the event of treatment interruption due to study-drug related toxicity, both agents will be held until the patient is able to resume further therapy. At the time of dosing resumption, alternate dose reduction strategy will be employed if the dose reduction is necessitated by hematologic toxicity. This alternate dose reduction will always start with Lenalidomide (not required if already at the minimum dose of 5mg) followed by Everolimus if further reduction is still necessary. In the case of non-hematological toxicity, dose reduction will be limited to the drug with the highest likelihood of attribution. In case of equal likelihood of attribution or where clear attribution is impossible, simultaneous reduction of both drugs will be effected at resumption of therapy.

NB: Patients unable to resume treatment within the allotted time period for recovery from treatment-related toxicities detailed in Table 5 and Table 6 may be allowed to resume treatment with express approval of the study sponsor provided they have evidence of clinical benefit from treatment and the toxicity has resolved to a level considered safe for further treatment with everolimus or lenalidomide. Also, patient may be allowed to continue on only one study drug if a permanent discontinuation of the other study drug is mandated by a unique treatment-related toxicity e.g. discontinuation of lenalidomide for desquamating rash.

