5.7.4 Monitoring of RAD001 suspected toxicities

Patients whose treatment is interrupted or permanently discontinued due to an adverse event or abnormal laboratory value suspected to be related to RAD001 must be followed at least weekly until the adverse event or abnormal laboratory resolves or returns to grade 1. If a patient requires a dose delay of > 21 days from the intended day of the next scheduled dose, then the patient must be discontinued from the study.

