5.11 Discontinuation of Study Treatment

Treatment will continue at the prescribed dose level until the occurrence of any of the following events.

- Disease progression
- Adverse event(s) that, in the judgment of the Investigator, may cause severe or permanent harm or which rule out continuation of the treatment regimen.
- Intolerance of lenalidomide or everolimus for any reason.
- Major violation of the study protocol.
- Withdrawal of consent
- Lost to follow up
- Death
 - Suspected pregnancy or positive pregnancy

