6.2.1 Pregnancies

Pregnancies and suspected pregnancies (including a positive pregnancy test regardless of age or disease state) of a female subject occurring while the subject is on lenalidomide, or within 28 days of the subject’s last dose of lenalidomide, are considered immediately reportable events. Lenalidomide is to be discontinued immediately. The pregnancy, suspected pregnancy, or positive pregnancy test must be reported to Celgene Drug Safety immediately by facsimile or email using the Pregnancy Initial Report Form. The female subject should be referred to an obstetrician-gynecologist, preferably one experienced in reproductive toxicity for further evaluation and counseling.

The Investigator will follow the female subject until completion of the pregnancy, and must notify Celgene Drug Safety immediately about the outcome of the pregnancy (either normal or abnormal outcome) using the Pregnancy Follow-up Report Form. If the outcome of the pregnancy was abnormal (e.g., spontaneous or therapeutic abortion), the Investigator should

report the abnormal outcome as an AE. If the abnormal outcome meets any of the serious criteria, it must be reported as an SAE to Celgene Drug Safety immediately by facsimile, or other appropriate method, within 24 hours of the Investigator's knowledge of the event using the SAE Report Form.

All neonatal deaths that occur within 28 days of birth should be reported, without regard to causality, as SAEs. In addition, any infant death after 28 days that the Investigator suspects is related to the in utero exposure to the IP should also be reported to Celgene Drug Safety immediately by facsimile, or other appropriate method, within 24 hours of the Investigator's knowledge of the event using the SAE Report Form.

Male Subjects

If a female partner of a male subject taking investigational product becomes pregnant, the male subject taking lenalidomide should notify the Investigator, and the pregnant female partner should be advised to call their healthcare provider immediately.

6.2.2 Celgene Drug Safety Contact Information:

Celgene Corporation
Global Drug Safety and Risk Management
[name]
[name]
[name]
[contact]
E-mail: [contact]

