- In addition to the required pregnancy testing, the Investigator must confirm with FCBP that she is continuing to use two reliable methods of birth control at each visit.
- Pregnancy testing and counseling must be performed if a subject misses her period or if her pregnancy test or her menstrual bleeding is abnormal. Lenalidomide treatment must be discontinued during this evaluation.

Male Subjects:

- Must agree to use a latex condom during sexual contact with females of childbearing potential while participating in the study and for at least 28 days following discontinuation from the study even if he has undergone a successful vasectomy.

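### Appendix B stops only lenalidomide while pregnancy is being evaluated; everolimus should be held too, and section 5.11 should say when treatment may resume

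*Combined protocol and SAP*

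**What the plan says.** Appendix B (section 13.2), in the part on female subjects during study participation, sets the trigger: "Pregnancy testing and counseling must be performed if a subject misses her period or if her pregnancy test or her menstrual bleeding is abnormal". The next sentence gives the action: "Lenalidomide treatment must be discontinued during this evaluation". Everolimus is not mentioned anywhere in the appendix.

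Section 5.11 lists the events that end study treatment, without naming a drug. One of them is "Suspected pregnancy or positive pregnancy". Nothing there says what happens if the suspicion proves unfounded.

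Section 6.2.1 makes "Pregnancies and suspected pregnancies (including a positive pregnancy test regardless of age or disease state) of a female subject" immediately reportable and stops lenalidomide. The everolimus pregnancy text in section 6.3 covers reporting and follow-up only.

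Section 5.7.3 does have a rule that suspends both drugs, but it applies in the event of "treatment interruption due to study-drug related toxicity, both agents will be held until the patient is able to resume". Section 5.3.5, on non-clinical toxicology, states: "Everolimus crossed the placenta and was toxic to the conceptus".

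**The concern.** The protocol records a fetal hazard for both drugs but writes the hold for one. Section 5.6.3 asks women of childbearing potential to wear gloves when handling either drug, so the everolimus hazard was recognised. Yet the instruction that a site would look up for a missed period or abnormal bleeding says nothing about swallowing everolimus while the answer is awaited.

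The general stopping rule in 5.11 may fill the gap, but a site must first decide that the woman's situation counts as a suspected pregnancy. It must then decide for itself whether she may restart after a negative result. Two sites, or two investigators, could reasonably act differently. At stake is avoidable everolimus exposure during a possible early pregnancy, and uncertainty about returning to treatment after a false alarm.

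**Working it through.** The plan gives no figure to reproduce on this point. The check is a comparison of the rules, followed by a short calculation of how fast each drug clears.

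**Which rule reaches which situation**

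| Situation | Appendix B | 5.11 | 6.2.1 | 5.7.3 |
|---|---|---|---|---|
| Missed period, no positive test | Lenalidomide stopped | Probably covered, if read as suspected pregnancy | Unclear | Not covered (not a drug toxicity) |
| Abnormal bleeding, no positive test | Lenalidomide stopped | Not clearly covered | Unclear | Not clearly covered |
| Positive test | Lenalidomide stopped | Study treatment stopped | Lenalidomide stopped | Not needed |

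1. For a positive test, 5.11 stops study treatment, which means both drugs. There is no gap in that row.
2. For the first two rows, the only rule that names the situation is Appendix B, and it stops lenalidomide only.
3. Section 6.2.1 says that suspected pregnancies include a positive test, so the category is wider than that. It does not say whether a missed period or abnormal bleeding belongs to it.
4. On resumption, the Appendix B stop lasts for the evaluation, which implies a restart but does not state one. Section 5.11 neither provides for a restart nor forbids it. The sponsor-approved route in 5.7.3 is for delayed recovery from treatment-related toxicity.

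**How fast each drug clears after a hold**

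Inputs: everolimus half-life of about 30 hours (5.3.2); lenalidomide half-life of 2.8 to 6.1 hours in myeloma patients (5.2.2). Assuming simple exponential decline, the share remaining after t hours is 2^(−t / half-life), whatever the dose.

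- Everolimus, 1 day: 2^(−24/30) = 0.574, or 57%
- Everolimus, 3 days: 2^(−72/30) = 0.189, or 19%
- Everolimus, 7 days: 2^(−168/30) = 0.021, or 2%
- Lenalidomide, 1 day: 2^(−24/2.8) = 0.0026 to 2^(−24/6.1) = 0.065, or 0.3% to 6.5%

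Without a hold, everolimus stays at its usual on-treatment level throughout. The documents do not give the length of an evaluation; 1 to 7 days is an assumed range.

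**How many patients**

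Section 10.6 gives a maximum of 45 patients, with 21 used in escalation: 45 − 21 = 24, which equals the two expansion groups, 15 + 9. These are patients of both sexes. Any escalation patient still on treatment would be added. The number of women of childbearing potential is not given.

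**Effect on the design**

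The Synopsis counts missed cycle 1 doses as a DLT only for "Inability to deliver all doses of Lenalidomide and or Everolimus during the first cycle due to an unexpected drug-related toxicity". A precautionary hold for a pregnancy evaluation is not that. Section 10.6 also describes the escalation count in the past tense.

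**The case against.** The strongest answer is that 5.11 already does the work. It ends study treatment as a whole, and it lists suspicion separately from a positive result, so suspicion must have a meaning of its own. A missed period that obliges a pregnancy test fits it naturally. On that view Appendix B is simply the lenalidomide programme text, and its silence on everolimus is a matter of scope. Much of this stands. A reader might infer that the protocol leaves everolimus running in every suspected pregnancy, and that is too strong: 5.11 plausibly stops it after a missed period. What 5.11 does not clearly reach is abnormal bleeding without a positive test, and Appendix B does not point the reader to it.

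A reader might also infer that 5.11 removes a woman from both drugs permanently on a false alarm. The documents do not support that either. Section 5.11 never says the stop is permanent and never bars a restart; it is silent.

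The size of the benefit can fairly be questioned. If a test result comes back within a day, the hold skips about one everolimus dose and 57% of the drug is still present. The sentence in 5.3.5 is non-clinical and follows rat fertility data. The clearance figures therefore describe exposure, not a measured fetal risk.

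Finally, the Revlimid REMS material is cited but not reproduced, so its conditions for restarting lenalidomide cannot be checked. The proposed wording defers to them.

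**Conclusion.** The point holds as a minor subject and fetal safety clarification. Followed literally, Appendix B continues everolimus while pregnancy is being excluded. Section 5.11 corrects this only if the site treats the situation as a suspected pregnancy, which is likely for a missed period and uncertain for abnormal bleeding. Neither place states when treatment may resume.

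The practical size is small: an everolimus exposure of perhaps a few days, in an unknown but small number of women among at most 24 further patients plus any still on treatment from escalation. The clearance figures rest on exponential decline and the stated half-lives, and the evaluation length is an assumption.

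Two wider inferences should be resisted. Positive tests and partner pregnancies are not unaddressed: 5.11 and 6.2.1 deal with a positive test in a subject, and Appendix B stops lenalidomide for a pregnancy in a subject or in a male subject's partner. Nor is there any consequence for sample size, power, error rates or the MTD decision.

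**What to change.** Replace the Appendix B sentence with:

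*Lenalidomide and everolimus must both be held during this evaluation; both may resume once pregnancy is excluded, subject to Revlimid REMS requirements and the 21-day delay limit in 5.7.4.*

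Add to 5.11:

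*If pregnancy is excluded after an Appendix B evaluation, treatment may resume as stated there; a positive test or confirmed pregnancy ends both drugs.*

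The 5.11 entry for suspected or positive pregnancy stays as it is, and so does the immediate lenalidomide stop in 6.2.1. Section 5.7.4 is written for suspected everolimus toxicity, so its limit (a delay of more than "21 days from the intended day of the next scheduled dose, then the patient must be discontinued from the study") has to be adopted by express reference, as above. No DLT wording is needed, because the existing definition already excludes such a hold.

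The cost is one sentence replaced and one added, in an amendment that the lenalidomide supporter reviews under 8.1 and the IRB approves. It adds no visit, test or patient; footnote 6 of the assessment schedule already continues pregnancy testing through breaks in therapy. The downside is a short everolimus interruption for a woman under evaluation, with some missed cycle 1 doses if it falls then.

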13.3 Appendix C NCI CTC Version 4.0

TOXICITY WILL BE SCORED USING NCI CTC VERSION 4.0 FOR TOXICITY AND ADVERSE EVENT REPORTING. A COPY OF THE NCI CTC VERSION 4.0 CAN BE DOWNLOADED FROM THE CTEP HOMEPAGE: ([HTTP://CTEP.INFO.NIH.GOV](http://CTEP.INFO.NIH.GOV)) OR [HTTP://CTEP.CANCER.GOV/PROTOCOLDEVELOPMENT/ELECTRONIC_APPLICATIONS/DOCS/CTCAEV4.PDF](http://CTEP.CANCER.GOV/PROTOCOLDEVELOPMENT/ELECTRONIC_APPLICATIONS/DOCS/CTCAEV4.PDF) .

ALL APPROPRIATE TREATMENT AREAS HAVE ACCESS TO A COPY OF THE CTC VERSION

13.4 Appendix D – Blood Sample Collection and Processing

Pharmacokinetic and Pharmacodynamic Studies

PK samples will not be collected during this study.

Flow Cytometry:

All patients will have blood samples collected for assessment of circulating lymphocytes as a pharmacodynamic endpoint for lenalidomide therapy. Samples will be collected at baseline and with the first 2 restaging scans for response assessment (on day 1 cycle 3 \pm 2days and day 1 cycle 5 \pm 2days;) and at the time of disease progression. Collect 5mls of whole blood in purple-topped tubes and invert gently several times to ensure appropriate mixing of blood and anticoagulant. Samples should be transported at room temperature to [name] lab on the 4th floor of the Winship Cancer Institute building (Attn: [name], MT, ASCP; Tel - [contact]).

ELISA Assay for circulating cytokines:

Samples for ELISA test should be collected in two red-topped tubes at baseline and with the first 2 restaging scans (day 1 cycle 3 \pm 2days and day 1 cycle 5 \pm 2days;) and at the time of disease progression if different than any of the aforelisted time points. Please transport samples on ice to the laboratory of [name] on the 3rd floor of the Winship Cancer Institute building, (Attention: [name] or [name]).

Tumor Biopsy

Patients enrolled in the expansion cohort must sign a separate informed consent form for research tumor tissue biopsy. Surgical tumor tissue and needle biopsies (collected by 18-gauge or larger needles), should be collected in pre-cooled cryovials and immediately flash frozen in liquid nitrogen, then stored at -80 degrees C. Samples will be sent to the laboratory of [name] (Attention: [name] or [name]) on the 3rd floor of the Winship Cancer Institute building.

13.5 Appendix E – List of CYP450 and PgP Interacting Drugs

Agents that may Increase Everolimus Blood Concentrations

CYP3A4 Inhibitors and PgP Inhibitors: In healthy subjects, compared to everolimus treatment alone there were significant increases in everolimus exposure when coadministered with: ketoconazole (a strong CYP3A4 inhibitor and a PgP inhibitor) - C_{max} and AUC increased by 3.9- and 15.0-fold, respectively; erythromycin (a moderate CYP3A4 inhibitor and a PgP inhibitor) - C_{max} and AUC increased by 2.0- and 4.4-fold, respectively; verapamil (a moderate CYP3A4 inhibitor and a PgP inhibitor) - C_{max} and AUC increased by 2.3- and 3.5-fold, respectively. Concomitant strong or moderate inhibitors of CYP3A4 and PgP inhibitors should not be used. Due to significant increases in exposure of everolimus, co-administration with strong or moderate inhibitors of CYP3A4 (e.g., ketoconazole, itraconazole, clarithromycin, atazanavir, nefazodone, saquinavir, telithromycin, ritonavir, amprenavir, indinavir, nelfinavir, delavirdine, fosamprenavir, voriconazole, aprepitant, erythromycin, fluconazole, grapefruit juice, verapamil or diltazem) or P-glycoprotein (PgP) should be avoided.

Agents that may Decrease Everolimus Blood Concentrations

CYP3A4 Inducers: In healthy subjects, co-administration of everolimus with rifampin, a strong inducer of CYP3A4, decreased everolimus AUC and C_{max} by 64% and 58% respectively, compared to everolimus treatment alone. An increase in the everolimus dose is recommended when co-administered with a strong CYP3A4 inducer (e.g., dexamethasone, phenytoin, carbamazepine, rifampin, rifabutin, phenobarbital).

Agents whose Plasma Concentrations may be Altered by Everolimus

Studies in healthy subjects indicate that there are no clinically significant pharmacokinetic interactions between everolimus and the HMG-CoA reductase inhibitors atorvastatin (a CYP3A4 substrate) and pravastatin (a non-CYP3A4 substrate) and population pharmacokinetic analyses also detected no influence of simvastatin (a CYP3A4 substrate) on the clearance of everolimus

Drug Interactions with Lenalidomide

Results from human in vitro metabolism studies and nonclinical studies show that lenalidomide is neither metabolized by nor inhibits or induces the cytochrome P450 pathway suggesting that lenalidomide is not likely to cause or be subject to P450-based metabolic drug interactions in man. Co-administration of multiple doses of 10 mg of lenalidomide had no effect on the single dose pharmacokinetics of R- and S-warfarin. Co-administration of single 25-mg dose warfarin had no effect on the pharmacokinetics of total lenalidomide. Expected changes in laboratory assessments of PT and INR were observed after warfarin administration, but these changes were not affected by concomitant lenalidomide administration. When digoxin was co-administered with lenalidomide the digoxin AUC was not significantly different, however, the digoxin C_{max} was increased by 14%. Periodic monitoring of digoxin plasma levels, in accordance with clinical

judgment and based on standard clinical practice in patients receiving this medication, is recommended during administration of lenalidomide.

